1 PROTOCOL SUMMARY

1.1 Synopsis

Name of Sponsor/Company: DMR Research, PLLC Sponsor: Endo Pharmaceuticals Inc.

Name of Investigational Product: Qwo CCH

Name of Active Ingredient: Collagenase clostridium histolyticum

Title of Study: Treatment of 5 subjects to assess the effectiveness of multiple dose, multiple concentrations of clostridium histolyticum-aases, QWO, for the treatment of mild to moderate cellulite in adult females to the buttocks and thighs.

Phase of development: 4

Lead Principal Investigator: [name] [name]

Study period:

Estimated date first subject enrolled: 15Feb2021 Estimated date last subject completed: 15May2021

Objectives and Endpoints:

objectives and Endpoints.				
Objectives	Endpoints			
Primary				
To assess the effectiveness of multiple dose, multiple concentrations of clostridium histolyticum-aases for the treatment of mild to moderate cellulite in adult females to the buttocks and thighs	The proportion of subjects with improved (+1 or better) score on the Investigator Global Aesthetic Improvement Scale (I-GAIS) for buttock and thigh at Day 90.			
Secondary				
To evaluate effectiveness of CCH-aaes in individuals when concomitantly treating the buttock and the thigh in one treatment session	The proportion of subjects with improved (+1 or better) score on I-GAIS for either buttock or either thigh on Days 22, 43, and 90.			
To assess subject satisfaction with CCH treatment of buttock or thigh cellulite in adult females.	Mean change from baseline in Body-Q Appraisal of Cellulite ^d to Day 90.			
To generate calculations to determine a matrix of buttock and thigh injections possible from a single 1.84 mg vial	Dilution matrix used in clinical settings.			

Overall Design:

This is a single center, off-label, multiple dose, multiple injection areas, Phase 4 study to assess the safety and efficacy of multi-dilution CCH in adult women with mild or moderate edematous fibrosclerotic panniculopathy (EFP). 5 subjects will be screened and dosed in the buttock and thigh areas using a multi-dilution injection technique.

Qualified subjects (determined by investigator assessment) will receive a single vial of 0.84 mg of CCH to treatment areas (buttocks and thighs) for a total dose of 1.68 mg in both buttocks and both thighs per treatment session \times 3 treatment sessions (Day 1, Day 22, and Day 43). Subjects will have follow-up visits at approximately 90 after Day 1.

1.2 Schedule of Activities

Table 1: Schedule of Activities

Activities	Screening (Day -14 to Day -1)	Day 1 (Treatment Session I)	Day 22 (+7 Days) (Treatment Session II)	Day 43 (+14 Days) (Treatment Session III)	Day 90 (+14 Days)
Informed consent ^a	Х				
Inclusion/exclusion criteria review ^b	Х	Х			
Medical and Surgical history	Х				
EFP history	Х				
Prior medications (including all prior medications for cellulite) ^b	Х	Х			
Physical examination	Х				Х
Height	Х				
Weight	Х	Х	Х	Х	Х
Fitzpatrick Skin Type	Х				
Hexsel CSS Subsection D ^b	Х				
Urine pregnancy test	Х	Х	Х	Х	Х
Body-Q Appraisal of Cellulited	Х				Х

^a Performed prior to any study-required assessments, unless exceptions granted for standard of care procedures.

^b Should be reassessed and verified prior to dosing.

^c Assessment should be completed independently of, and prior to, any investigator cellulite assessments (CR-PCSS, I-GAIS, Investigator Satisfaction with CCH).

^d Before and after marking target dimples at treatment visits. No manipulation of the treatment area should be done prior to the "before" images.

^e CR-PCSS-Buttock and CR-PCSS-Thigh will both be done at screening.

^f I-GAIS will be completed after CR-PCSS when both are required at the same visit.

^g AEs/SAEs will be captured from the time of informed consent signature until the Day 90/Early Termination Visit or until 28 days after last dose of study drug whichever is later. There is no time limit on collection of

SAEs felt to be related to study treatment.

Note: Unless otherwise stated above or outlined below (and with the exception of injection site reactions/local tolerability in the areas treated), all assessments

should be completed prior to dosing on treatment days (Days 1, 22, and 43).

2. INTRODUCTION

QwoTM (CCH) is a parenteral lyophilized product comprised of 2 collagenases in an approximate 1:1 mass ratio, Collagenase I (Clostridial class I collagenase [AUX-I]) and Collagenase II (Clostridial class II collagenase [AUX-II]). Qwo is an FDA-approved injectable for moderate to severe cellulite in the buttocks of adult women. QWO targets a primary structural cause of cellulite – the fibrous septae.1,2

2.1 Study Rationale

The results from phase 3b EN3835-305 received FDA approval of Qwo for 3-aliquot injection technique in buttocks (up to 12 injections x 0.23 mg/mL x 0.3 mL/injection = 0.84 mg/buttock). Study EN3835-305 uses a 5-aliquot injection technique for treatment of thighs (up to 12 injections x 0.047 mg/mL x 1.5 mL/injection = 0.84 mg/thigh)(Palm ASDS 2020; Gold VCS2020) EN3835-305 administered subjects in either buttock (with 3-aliquot) technique or thigh (with 5-aliquot technique) using sterile saline. The purpose of this study is to determine the mechanics and effectiveness of treating cellulite subjects with both the 3-aliquot technique in the buttock and 5-aliquot technique in the thigh during the same treatment session without compromising effectiveness of treatment.

2.2 Background

Collagenase clostridium histolyticum-aaes is a combination of bacterial collagenases AUX-I and AUX-II, in an approximate 1:1 mass ratio, which are isolated and purified from the fermentation of Clostridium histolyticum bacteria. Collagenase AUX-I is a single polypeptide chain consisting of approximately 1000 amino acids. Collagenase AUX-II is a single polypeptide chain consisting of approximately 1000 amino acids.

QWO (collagenase clostridium histolyticum-aaes) for injection is supplied as a sterile, preservative-free, lyophilized powder (appearing as a white cake) in single-dose vials for subcutaneous use after reconstitution with the Diluent for QWO.

To investigate the effectiveness and feasibility of multiple dose, multiple concentrations of clostridium histolyticum-aases for the treatment of mild to moderate cellulite in adult females to the buttocks and thighs

More specifically, to evaluate effects of CCH-aaes in individuals when concomitantly treating the buttock and the thigh in one treatment session:

- with 3-aliquot injection technique (0.23 mg/mL x 0.3 mL/injection) in buttock using supplied diluent
- with 5-aliquot injection technique (0.047 mg/mL x 1.5 mL/injection) in thigh using sterile saline to dilute

2.3 Risk/Benefit Assessment

Current treatments for EFP have limited efficacy and undesirable side effects. There remains an unmet need for safe and effective nonsurgical therapies to improve the aesthetic outcome in women with cellulite.

The following AEs have been commonly observed in subjects treated with CCH for EFP: local injection site reactions including injection site bruising, injection site swelling, and injection site pain. These events are similar to events reported in the clinical trials of EN3835 for the approved indications. Postmarketing safety data are consistent with safety data reported in clinical trials.

More detailed information about the known and expected benefit, risks, and reasonably expected AEs associated with CCH can be found in the current version of the Investigators Brochure.

3. OBJECTIVES AND ENDPOINTS

Objectives	Endpoints
Primary	
	better) score on the Investigator Global Aesthetic Improvement Scale. (I-GAIS) for buttock and thigh
Secondary	
To evaluate effectiveness of CCH-aaes in individuals when concomitantly treating the buttock and the thigh in one treatment session	The proportion of subjects with improved (+1 or better) score on I-GAIS for either buttock or either thigh on Days 22, 43, and 90.
To assess subject satisfaction with CCH treatment of buttock or thigh cellulite in adult females.	Mean change from baseline in Body-Q Appraisal of Cellulite ^d to Day 90.
To generate calculations to determine a matrix of buttock and thigh injections possible from a single 1.84 mg vial	Dilution matrix used in clinical settings.

4. STUDY DESIGN

4.1 Overall Design

Treatment of 5 subjects to assess the effectiveness of multiple dose, multiple concentrations of Qwo, clostridium histolyticum-aases for the treatment of mild to moderate cellulite in adult females to the buttocks and thighs.

The concept of this study would be to determine the effectiveness of treating multiple areas simultaneously by diluting with company provided diluent to buttock concentration, treating buttocks dimples appropriately with accepted injection technique and then diluting remaining CCH-ases with sterile saline to appropriate thigh concentration. Thigh dimples will then be treated with standard injection technique as in EN3835-305 Phase 3b.

Reconstitution prep and injection technique

Buttock - on label; importantly will be dosed first

- Reconstitution: 1.84 mg reconstitution with 8 mL of supplied diluent = 0.23 mg/mL
- Use up to 3.6 mL for buttock injections dependent on number of dimples (injections) present

Thigh

- Reconstitution (EN3835-305 approved dilution technique); to the 0.047 mg/mL concentration with sterile saline
- Based on how many buttock injections to were performed, the remaining 0.23mg/mL solution will be diluted 5-fold with sufficient sterile saline to yield 0.047 mg/mL concentration necessary for thigh
- Based on the final volume generated from 5-fold dilution of the 0.23 mg/mL retain will determine the number of injections possible in thigh

Scientific Rationale for the Study Design

This is an off-label exploratory study to determine proper dilution techniques of CCH in EFP to be used in clinical practices.

4.2 Justification for Dose

The results from a Phase 2b study (EN3835-201) suggested that CCH 0.84 mg per treatment area (1 buttock or 1 thigh) is safe and effective. The Phase 3 studies (EN3835-302, EN3835-303 and EN3835-305) using the same dose in each buttock showed a similar safety profile with most AEs being mild to moderate in severity and transient. The immunogenicity profile of CCH has been consistent across all clinical studies to date. Therefore, the dose of 0.84 mg per treatment area (each buttock or each thigh – for a total dose of 1.68 mg of CCH for 2 buttocks and 2 thighs) will be used in this study.

4.3 End of Study Definition

A subject is considered to have completed the study if the subject has completed the Day 90 visit.

The end of the study is defined as the completion of the final assessment for the last subject enrolled in the trial.

5. SELECTION AND WITHDRAWAL OF SUBJECTS

5.1 Subject Inclusion Criteria

In order to be eligible to participate in the study, at the Screening Visit and on Study Day 1, subjects must:

- 1. Be female and 18-60 years of age at the time of consent.
- 2. Have both buttocks and both posterolateral thighs with:
- a. A score of 2 or 3 (mild or moderate) as reported by the investigator using the Clinician-Reported Photonumeric Cellulite Severity Scale (CR-PCSS).
- b. A Hexsel Cellulite Severity Scale (CSS) Subsection D "Grade of Laxity, Flaccidity, or Sagging Skin" score of 0 (absence of laxity, flaccidity, or sagging skin), or 1 (slightly draped appearance) at the Screening Visit only.
- 3. Have a body mass index (BMI) score between 18.0 kg/m² and 30.0 kg/m² and intends to maintain stable body weight (:S10% change from the Day 1 Visit weight) throughout the duration of the study (from the Screening Visit through the Day 180/Early Termination Visit).
- 4. Be willing to apply sunscreen to the treatment areas before each exposure to the sun for the duration of the study (from the Screening Visit through the Day 180/Early Termination Visit).
- 5. Be judged by the investigator to be in good health, based upon the results of a medical history and physical examination,.
- 6. Be of nonchildbearing potential (history of hysterectomy, bilateral oophorectomy, bilateral tubal ligation, or postmenopausal with no history of menstrual flow in the 12 months prior to the Screening Visit); or, if of childbearing potential, be nonpregnant, nonlactating, and agree to use effective contraception when with a male partner for the duration of the study. Acceptable forms of contraception include hormonal measures (oral contraceptive pills, contraceptive patch, contraceptive ring, injections, etc), intrauterine devices, double barrier method (condom plus diaphragm, condom or diaphragm plus spermicidal gel or foam), surgical sterilization of the male partner, and abstinence.
- 7. Have a negative serum pregnancy test at the Screening Visit and a negative urine pregnancy test prior to dosing at each treatment session.
- 8. Be willing and able to comply with all protocol required visits and assessment Be able to read, understand, and independently complete patient reported outcome instruments in English.
- 9. Be able to read, understand, and independently complete patient reported outcome instruments in English.
- 10. Be adequately informed and understand the nature and risks of the study and be able to provide consent as outlined in Section 10.1.3.

5.2 Subject Exclusion Criteria

A subject is ineligible for study participation if, at the Screening Visit or on Day 1, the subject:

1. Is from a vulnerable population, as defined by the United States (US) Code of Federal Regulations (CFR) Title 45, Part 46, Section 46.111(b) and other local and national regulations, including but not limited to, employees (temporary, part-time, full-time, etc) or a family member of the research staff conducting the study, or of the sponsor, or of the contract research organization, or of the Institutional Review Board (IRB)/Independent Ethics Committee (IEC).

- c. Has a history of sensitivity or allergy to collagenase or any other excipient of CCH.
- d. Has any of the following systemic conditions:
- 1. Coagulation disorder.
- 2. Evidence or history of malignancy (other than excised basal-cell carcinoma) unless there had been no recurrence in at least 5 years.
- 3. History of keloidal scarring or abnormal wound healing.
- 4. Concurrent diseases or conditions that might interfere with the conduct of the study, confound the interpretation of the study results, or endanger the subject's well-being. Any questions about concurrent diseases will be discussed with the Medical Monitor.
- 5. Evidence of clinically significant abnormalities on physical examination, vital signs, , or clinical laboratory values.
- e. Has any of the following local conditions in the areas to be treated (both buttocks or both thighs):
- 1. History of lower extremity thrombosis or post-thrombosis syndrome.
- 2. Vascular disorder (eg, varicose veins, telangiectasia).
- 3. Inflammation or active infection.
- 4. Active cutaneous alteration including rash, eczema, or psoriasis.
- 5. A tattoo or other artificially inflicted body marker.
- 6. Has a mole located within 2 cm of any injection site.
- f. Has skin laxity or linear undulations on the treatment region (both buttocks or both thighs) that can be effaced by lifting skin.
- g. Has a Hexsel CSS Subsection D "Grade of laxity, flaccidity, or sagging skin" of 2 (moderate draped appearance) or 3 (severe draped appearance).
- h. Requires anticoagulant or antiplatelet medication during the study or has received anticoagulant or antiplatelet medication (except for :S150 mg aspirin daily) within 7 days before injection of study treatment.
- i. Has used any of the following for the treatment of EFP on either thigh and either buttock within the timelines identified below or intends to use any of the following at any time during the course of the study:
- j. Liposuction during the 12-month period before dosing with study treatment.
- k. Injections (eg, mesotherapy, dermal fillers, biostimulatory fillers); radiofrequency device treatments; laser treatment; buttock and thigh implant treatment; cryolipolysis; or surgery (including subcision and/or powered subcision) during the 12-month period before injection of study treatment.
- 1. Any investigational treatment for EFP on a buttock and thigh during the 12-month period before the injection of study treatment.
- m. Endermologie or similar treatments during the 6 month period before injection of study treatment.

- o. Massage therapy during the 3-month period before injection of study treatment. Creams (eg, Celluvera[™], TriLastin[®]) and/or home therapies to prevent or mitigate EFP during the 2-week period before injection of study treatment.
- p. Has received any collagenase treatments at any time prior to treatment in this study and/or has received previous treatment with EN3835 or CCH for cellulite.
- q. Has received treatment with an investigational product within 30 days (or 5 half-lives, whichever is longer) of the Screening Visit.
- r. Is pregnant and/or is providing breast milk or plans to become pregnant and/or to provide breast milk during the course of the study.
- s. Intends to initiate an intensive sport or exercise program during the study.
- t. Intends to initiate an intensive weight reduction program during the study.
- u. Has any other condition(s) that, in the investigator's opinion, might indicate the subject to be unsuitable for the study.

6. Lifestyle Considerations

See Section 5.1 and Section 5.2.

6.1 Screen Failures

Screen failures are defined as subjects who consent to participate in this study but are not subsequently treated. Eligibility confirmation by the sponsor or designee is required for this study (see Section 8.1).

Subjects who do not meet all of the eligibility criteria at the Screening or Day 1 Visits will be deemed a screen failure and the following information must be recorded for all subjects who are screen failures:

- Demography (age, gender, race/ethnicity).
- Reason for screen failure.
- Which eligibility criterion was not met.

7. STUDY TREATMENT

Study treatment is defined as any investigational treatment, marketed product, placebo, or device intended to be administered to a study subject according to the study protocol.

7.1 Selecting and Marking Target Dimples for Treatment

For treatment, the investigator or qualified designee will select up to 12 dimples within each treatment area (each buttock or each thigh) that are well-defined, evident when the subject is standing, and suitable for treatment. These dimples will be designated as the target dimples and will be treated at each treatment session (Days 1, 22, and 43) as long as they remain visible. Dimples in the buttock will be treated first and will not exceed the maximum amount of 12 dimples. After the buttock treatment, the dilution matrix will be utilized to determine the dilution ratio for the thigh treatment area. The maximum dose per treatment area (each buttock or each thigh) will not exceed 0.84 mg.

For each target dimple selected for treatment, the investigator or qualified designee will choose

injection sites (injection sites within a dimple should be spaced approximately 2 cm apart, if a dimple requires more than 1 injection; locating at least one injection site at the nadir, if present, of the dimple). Each injection site will be marked with a "dot" using a surgical marker. For round dimples, the "dot" will be placed in the center of the dimple; for elongated dimples, "dots" will be spaced out approximately 2 cm along the longer axis of the dimple. The investigator or qualified designee will then use a surgical marker to circle each of the target dimples selected for treatment.

7.3 Table 2: Study Treatment

a. The proposed maximum number of injections sites per treatment area has been determined based on safety data of 0.84 mg/treatment area.

b. A maximum of up to 26 injections can be administered throughout the treatment sites

NOTE: CCH is a foreign protein and investigators must be prepared to address and manage an allergic reaction should it occur. At the time of each injection, a 1:1,000 solution of epinephrine for injection, 50-mg diphenhydramine injection or a suitable equivalent, and oxygen must be available and the investigator and site staff must be familiar with their use. To evaluate the subject for possible immediate immunological AEs, the subject will remain in direct observation of medical personnel who are skilled in the management of an allergic reaction for 30 minutes after receiving the injections of study treatment and until the subject exhibits no sign of an immunological or other clinically significant systemic or local AE. The subject's vital signs should be stable before the subject can leave direct observation.

After the completion of dosing at each treatment session, the investigator or qualified designee will apply a sterile dressing to the injection areas with hypoallergenic tape. The subject will be instructed to remove the dressing in the evening.

At the discretion of the investigator, compression at the treatment area may be recommended to the subject. If compression at the treatment area is used by the subject, the start and stop date and type of compression used will be recorded in the source documents and the eCRF.

7.4 Study Treatment Preparation/Handling/Storage/Accountability

Vials of 1.84 mg Qwo CCH will be supplied to the site. Each vial of Qwo will be labeled with contents, sponsor identification, storage, administration/use, and appropriate caution statements. CCH and the diluent must be stored in an appropriate, secure area. Study treatment must be kept in a temperature-monitored refrigerator (2°C to 8°C) with locked access until used or returned to Endo.

The investigator or designee will confirm that appropriate temperature control conditions have been maintained during transit for all study treatments received and that any discrepancies are reported and resolved prior to study treatment administration.

Only subjects enrolled in the study will receive study treatment and only authorized study staff will dispense study treatment.

In accordance with the International Council for Harmonisation (ICH) requirements, at all times the investigator will be able to account for all study treatment furnished to the study site. An accountability record will be maintained for this purpose. The investigator must maintain accurate records indicating dates and quantity of study treatment received, to whom it was administered (subject-by-subject accounting), and accounts of any study treatment accidentally or deliberately destroyed. All unused study treatment not involved in immediate subject treatment will be maintained under locked, temperature-controlled storage at the study site.

Please refer to the Pharmacy Manual for complete information regarding preparation, handling, storage, and accountability of study treatment.

7.5 Measures to Minimize Bias

This is an open label, nonrandomized study; measures to minimize bias using treatment blinding or randomization are not applicable to this study.

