7.6 Study Treatment Compliance

All subjects will receive study treatment administered by the investigator at the study site. All dosing information will be recorded for each subject visit. Drug inventory will be maintained in the IRT system for each site, and all original containers of used and unused study treatment and diluent will be returned to the sponsor (or designee) at the end of the study.

Accidental or intentional overdoses should be reported to the sponsor/designee promptly (see Section 8.5).

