9.2.1 Imaging for Outcome Assessments

Although digital photographs are not direct efficacy measurements, digital photography will be utilized in the assessment of certain efficacy measurements (ie, to assess certain cellulite severity parameters at specific intervals). At screening, the investigator or qualified designee will photograph each of the 2 treatment areas (both buttocks and both thighs) independently using a sponsor-supplied standardized digital camera in a standardized manner. For subsequent visits only the areas receiving treatment (both buttocks or both thighs) will be photographed. The subject will be standing in a consistent, relaxed standing pose (ie, standing position with relaxed gluteus muscles) for each photography session and will be wearing a standardized photographic garment as described in the Photography Manual. These photographs will be taken before and after marking of the treatment area for dosing at treatment visits.

All photographs from this study are the property of Endo and de-identified images may be utilized for clinical development, scientific communication, marketing, regulatory purposes, and/or legal applications as required/desired by Endo.

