9.2.7 Investigator Global Aesthetic Improvement Scale

Investigators who are physicians will use the I-GAIS to determine the degree of improvement of each buttock or thigh by comparing the cellulite from the Day 1 pretreatment (baseline) outcome image of each buttock or each thigh to the images taken at the subsequent visits specified in the Schedule of Activities. In visits where both I-GAIS and CR-PCSS are scheduled, I-GAIS assessment will occur after the CR-PCSS assessment to avoid introducing potential bias to the static CR-PCSS assessment by the investigator.

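### Treatment cannot be blinded in this single-arm study, but the primary I-GAIS rating compares photographs and could be masked to visit; Section 7.5 stops short of this.

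*Protocol*

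**What the plan says.** Section 7.5 is the protocol's section on bias control. Beyond stating that the study is open label and nonrandomized, it says only that "measures to minimize bias using treatment blinding or randomization are not applicable to this study".

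The synopsis defines the primary endpoint as the share of subjects who score +1 or better on I-GAIS, for buttock and thigh, at Day 90. Section 10.3.1 summarizes it as one proportion with a 95% confidence interval, counting a subject as a responder if any buttock or thigh responds. No comparator or reference rate is given.

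Section 9.2.7 names the rater: "Investigators who are physicians will use the I-GAIS to determine the degree of improvement". It describes the method as "comparing the cellulite from the Day 1 pretreatment (baseline) outcome image of each buttock or each thigh", with photographs from later visits as the other side of the comparison. Section 7.6 says who injects: "All subjects will receive study treatment administered by the investigator at the study site". The synopsis describes a single center.

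On photographs, Section 9.2.1 states: "At screening, the investigator or qualified designee will photograph each of the 2 treatment areas (both buttocks and both thighs) independently", with standardized camera, pose and garment. It adds that "These photographs will be taken before and after marking of the treatment area for dosing at treatment visits". The Schedule of Activities places screening between Day -14 and Day -1, so screening and Day 1 pre-dose images are separated only by an untreated interval.

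**The concern.** The stated primary objective is effectiveness, and the evidence for it is an investigator's judgement that one image looks better than another. The person judging knows which image is the baseline and which follows treatment. The protocol gives injection and rating to the same role at one center. There is no second arm and no rating of an untreated pair, so nothing in the data shows how often this rater would score +1 when no drug lies between two images.

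The confidence interval in Section 10.3.1 covers sampling error only; it carries no information about this source of error. Who rates, when, and with what labels is study conduct fixed in Section 9.2.7. A later analysis plan cannot mask ratings already made with the visit known.

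**Working it through.** The plan states no figure on this point, and Section 10.1 gives the sample size of 5 without inputs, so there is nothing to reproduce. The check has three parts.

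**1. Can the rating be masked with what is planned?**

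- Image against image: yes (9.2.7).
- Untreated image of both buttocks and both thighs: yes, at screening (9.2.1).
- Images free of surgical marks: yes, the before-marking set at treatment visits (9.2.1).
- Day 90 image: inferred from 9.2.7, because the imaging and I-GAIS rows are not visible in the copy of the Schedule of Activities reviewed.
- Does any treatment decision need I-GAIS during the study? None is stated. Under Section 7.1, target dimples are re-treated while they remain visible, which does not use I-GAIS.
- Do existing safeguards already mask the rater? No. Section 9.2.2 separates subject from investigator ratings, and 9.2.7 places I-GAIS after CR-PCSS to protect CR-PCSS. Neither hides the visit.

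**2. How large could the effect be?** Let q be the chance of a false +1 on one area with no true change. The documents give no value; 5%, 10% and 20% are assumptions.

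- Any of four areas, independent: 1 − (1 − q)^4.
- Any of four areas, fully correlated: q.
- At least one buttock and at least one thigh, independent: (1 − (1 − q)^2)^2. The synopsis wording may be read this way.

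| q | Any area, fully correlated | Any area, independent | Buttock and thigh, independent |
|---|---|---|---|
| 5% | 5% | 1 − 0.95^4 = 18.5% | 0.0975^2 = 1.0% |
| 10% | 10% | 1 − 0.90^4 = 34.4% | 0.19^2 = 3.6% |
| 20% | 20% | 1 − 0.80^4 = 59.0% | 0.36^2 = 13.0% |

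If areas are fully correlated, the buttock-and-thigh rule also gives q. At q = 20% under the any-area rule, the chance of at least 3 of 5 responders with no drug effect is 0.06 if fully correlated and 0.67 if independent.

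**3. What would the screening pairs deliver?** There are 5 subjects × 4 areas = 20 untreated pairs. With no false +1 among them, the exact two-sided 95% upper limit is 1 − 0.025^(1/20) = 16.8% if all 20 are independent. Counted by subject (0 of 5), it is 1 − 0.025^(1/5) = 52.2%. This is a descriptive reference and cannot serve as a test.

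**The case against.** **Section 7.5 is accurate.** A reader might infer that the section is false. It is not: it speaks of treatment blinding and randomization, and neither applies to one open-label arm. What stands is that masking the assessor is a separate measure, is feasible here, and is not mentioned.

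**Rating instructions may sit elsewhere.** Section 9.2 leaves specific instructions to a Study Operations Manual, and 9.2.1 refers to a Photography Manual. Neither is available for review. The protocol itself describes no masking.

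**Bias controls exist.** Standardized imaging does limit photographic variation, and ratings are kept separate from the subject's own. This reduces the problem but does not hide the visit from the rater.

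**The error is not one-directional.** A reader might infer that it can only flatter the product. Photographic variation can also hide a real +1. Only for a subject with no true response does any-area scoring register upward error alone.

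**The independent-areas figures are the upper end.** A reader might take 59% as the size of the bias. Expectation belongs to one rater and is likely to be shared across areas of one subject, which moves the figure towards q itself. Every q is assumed.

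**The study is small and exploratory.** It has 5 subjects and no success threshold. Even 5 of 5 responders gives an exact interval of 47.8% to 100%. This limits the weight of the point, but the remedy is correspondingly cheap.

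**Conclusion.** The point holds as a cheap improvement to the primary endpoint. As written, rater expectation and photographic variation cannot be separated from treatment effect, because images known to be post-treatment are rated against a known baseline with no untreated reference. The documents do not show that expectation has produced, or will produce, any particular share of responders; the size is unknown.

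Under assumed per-area false rates of 5% to 20%, the subject-level false response under the Section 10.3.1 rule runs from 5% to 20% with full correlation and from 19% to 59% with independence. It is lower than the independent any-area figures if a buttock and a thigh must both respond.

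A reader might also infer that rating the screening pairs would estimate the false-positive rate of the current unmasked procedure. It would not. It measures error under masked reading, in 20 pairs clustered in 5 subjects, over at most 14 days.

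The verdict assumes that unmarked images of all four areas exist at screening, Day 1 and each later visit.

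**What to change.** In Section 9.2.7:

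- Have the same investigator rate I-GAIS after the last Day 90 visit, from the existing images without surgical marks.
- Keep the Day 1 image as the labelled reference.
- Show the screening, Day 22, Day 43 and Day 90 images without visit labels and in random order.
- Report the share of screening-versus-Day 1 pairs rated +1 or better beside the Day 90 proportion, stated to be a descriptive reference only.

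Amend Section 7.5 to say that treatment is open but the I-GAIS reading is masked to visit.

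The cost is about 20 extra ratings and the relabelling and shuffling of files by existing staff. No subject, visit or photograph is added.

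Downsides to state openly:

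- Ratings come at the end of the study.
- Masking is partial if bruising shows or the investigator recognizes a subject, which is likely enough with 5 subjects and one rater.
- The untreated interval is at most 14 days, so it does not capture natural change over 90 days.
- The reference rate will be imprecise.
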